## **5.7 Other samples**

All samples will be collected according to recognised guidelines, stored under appropriate conditions and in line with all relevant legislation, and tested and analysed using documented protocols and procedures. The Executive Board will regularly review the ongoing blood sample collection, storage, processing and analysis. Processing of samples for gene expression, epigenetics, telomere length, proteomics and other biomarkers will be subject to funding.

### **5.8a Data-analysis of the semi-structured interviews**

Audio-recorded interviews will be conducted privately face to face or via telephone between the participant and an interviewer after informed consent. The interviews would be anticipated to be between 30 minutes and one in hour duration and will be professionally transcribed verbatim, with identifiable information removed. Interview prompts will be devised based upon relevant literature, experience of the team and consultation with patient representatives.

The interviews will be reviewed using thematic analysis supported by NVivo software. This approach follows six distinct stages: familiarisation with data; generating initial codes; searching for themes; reviewing themes; defining and naming themes and producing the report. Initial coding will be carried out and a sample of interviews will be coded by a second member of the team to ensure consistency and to enhance interpretive authenticity. Throughout the data analysis, an iterative approach will be undertaken with the research team meeting to discuss and review emerging themes and search for accounts that provide contesting views of the same phenomena or identify different phenomena. Patient representatives will be invited to comment on the emerging themes from the patient interviews to whether important issues may have been missed which could be included in subsequent interviews.

Audio recordings will be conducted using an encrypted Dictaphone. The recordings will be uploaded to secure drives on University of Leicester and University Hospitals of Leicester computers then deleted from the Dictaphone. Access to the files will be restricted and password protected. The transcription will be performed by an external company and a confidentiality agreement will be in place.

### **5.8b Data-analysis of physical activity monitoring**

Data will be downloaded from the activity monitors at the recruiting site and then transferred to the NIHR Leicester BRC lifestyle team in line with their written standard operating procedure. Data will be processed to provide validated objective measures of sleep duration and quality, sedentary behaviour, time in different intensities of physical activity, as well as overall physical activity volume and intensity profiles using methods and standard operating procedures developed within the Lifestyle theme of NIHR Leicester BRC.

## **6. ELIGIBILITY**

### **6.1 Overall Description of Eligible Participants**

All patients who are admitted to an admissions unit or ward at UK recruiting hospital sites will be invited to join the study following discharge from hospital with clinician suspected COVID-19. This will include eligible individuals who were discharged from hospital before the start of the study (see [Error! Reference source not found.](#)).

### **6.2 Inclusion Criteria**

- Participant admitted to an admissions unit or ward at a UK hospital and discharged with suspected COVID-19
- Participant or consultee is willing and able to give informed consent for participation in the study
- Aged 18 years or above.

### **6.3 Exclusion Criteria**

- Confirmed diagnosis of a pathogen unrelated to the objectives of this study and no indication or likelihood of co-infection with a relevant pathogen.
- Attendance at an A&E or emergency department only
- Refusal by participant, parent or appropriate representative.
- Other life limiting illness with life expectancy <6 months such as disseminated malignancy.

### **6.4 Participation in other studies**

Patients who have already consented to COVID-19 related research (e.g., ISARIC-4c and RECOVERY trials) are eligible for inclusion. As this is an observational study participation in other studies is permitted, at the discretion of the investigators. The investigators will consider the burden of assessment of such participation for individual patients.

We will seek consent for linkage of all data and samples obtained for research purposes from participants who have or will provide consent to more than one COVID-19-related research study or longitudinal population study.

## 7. STUDY PROCEDURES

### 7.1 *Informed Consent*

Patients will be provided with a copy of the Participant Information Sheet and consent form upon discharge from hospital or after healthcare professional contact within 12 months of discharge. Eligible participants will be identified by their normal clinical care team either directly by the participating site or via participant identification centres (PIC) sites. If identified via a PIC site and the patient is interested in taking part, then a member of the clinical care team will provide the patients details to the PHOSP study team at the local participating site, or the patient can contact the local study team directly using the contact details on the information sheet. Study information may be provided to potentially eligible participants either directly to the patient during a hospital/clinic visit or by post with an accompanying invitation letter. A phone number for contact for further information and the procedure for withdrawal is provided as part of the Participant Information Sheet. Study information, such as the study leaflet, may also be placed publicly available at participating sites and PIC sites (for example waiting areas).

Participants have the option to provide informed consent in one of four different ways:

- **Face-to-face** with a healthcare professional/member of the research team at a hospital appointment
- By **Telephone** with the support of a healthcare professional/member of the research team, or
- By **Post**
- By e-consent

We will not require potential participants to have been given 24 hours to review the Participant Information Sheet.

Patients choosing to provide informed consent by either the **face-to-face** or **postal** methods will sign a consent form that will be counter-signed by a member of the research team (at the same time or upon receipt if returned by post). A fully signed copy of the consent form will be provided to the participant for their records either at the time of their face-to-face consent, or by return post together with a copy of the withdrawal form.

NB. Postal Consent is the least preferred method of consent for PHOSP-COVID due to previously returned postal consent forms being incomplete and inaccurate. Any postal consent received at site must be checked thoroughly to ensure it is complete and accurate. Follow-up with participants may be required.

Patients choosing to provide consent by the **Telephone** method will have each statement on the Consent Form read to them by a member of the research team in conjunction with additional information about the study as required. The researcher will obtain verbal assent from the patient for each statement and then initial against each statement to confirm it has been understood and agreed to. The researcher will sign the consent form confirming that full verbal assent has been provided for the study, and a copy will be posted to the participant together with a copy of the withdrawal form.

Patients will also have the option to consent electronically via the e-consent system. All patients invited to join the study will receive details and instructions on the invitation letter, providing them with

access to the e-Consent system. Patients choosing to provide consent by e-Consent will be asked to follow the URL: [phosp.org/consent](http://phosp.org/consent). There they will be asked to enter a 6 digit code (provided on the invitation letter), their first name, last name, year of birth and recruiting site (provided on the invitation letter). Error messages will appear if the invitation code/site is incorrect or the first name/last name is incorrect. All fields will need to be completed before they can proceed. This will take them to the e-consent platform where they will follow the instructions and complete the consent and some further questions. These additional questions are normally completed by the research team, but participants have the option to complete these via the e-consent platform. The electronic consent form will require the participant to confirm in the affirmative each mandatory statement from the consent form and provide an affirmative or negative response to the optional statements. At the end of the form the system will request the participant to provide an electronic signature (and witness/ translator signature if required) and then provide them with a downloadable pdf of their completed consent. If the patient chooses not to consent they will reach a page informing them that they chose not to take part. A section of the website will be available for participants to access using their 6 digit code where they can access a generic and current PIS and withdrawal form and their local hospital site contact details. Patients who complete the e-Consent will have their data automatically allocated to their appropriate recruiting site in the REDCap database, and an alert will go to a member of the appropriate study team notifying them that a patient has completed e-Consent, where it can be reviewed for completeness. If a patient is taking part, the patient can then be allocated a PHOSP ID by the recruiting site.

To generate the 6 digit codes, the PHOSP recruiting sites will go to [phosp.org/redcap/phosp-econsent-invitation-code-generation](http://phosp.org/redcap/phosp-econsent-invitation-code-generation). There they will upload an Excel file containing the details of patients who will be invited to use e-Consent for the PHOSP study. The Excel file requires patient first name, last name, and year of birth. The recruiting site also selects their site from the dropdown list and uploads the file. They will then be able to automatically download a csv file which contains a 6 digit code to be added to the patient's invitation letter.

Patients can opt-out of DNA collection and Tier 2 research data collection and still contribute Tier 1 research data.

At subsequent face-to-face visits, continued willingness to participate will be confirmed verbally by the research team and documented. Participants will have received a copy of the withdrawal form following informed consent, however, we will also host the withdrawal form on [Phosp.org](http://Phosp.org) so it is accessible to all participants.

Patients who are unable to sign the consent form themselves either due to physical or language difficulties but are able to provide informed consent may do this through a **witness/translator** whose relationship to the participant should be documented on the consent form and who should sign the appropriate declaration on the consent form. A witness/translator can be a family member or trusted friend, member of the research team, a healthcare professional, or a routine hospital translator. For those participants who consented to the study via a witness/translator and are participating in any Tier 2 research visits, the study team will make every effort to ensure that the participant fully understands their involvement in the study and provides continued willingness to participate. This will be documented.

**Consultee Declarations** will be allowed for **Tier 1 recruitment only** for patients who do not have capacity (temporarily or permanently) to provide consent themselves. There are a number of different ways these participants will be identified:

- 1) a representative contacting the study team follow an invitation letter being sent to the patient

2) by a treating clinician contacting the study team

[figure not shown]
3) where permission is available to contact the patient directly but it becomes apparent to the study team that the patient may lack capacity (and this would then be clarified by a clinician)

A clinician experienced in assessing capacity will decide if a patient has capacity to provide consent. A Consultee can be a Personal Consultee or a Nominated Consultee. A **Personal Consultee**, who is someone who cares for the patient or is interested in their welfare, has a personal relationship with the patient and does not have a conflict of interest, such as being part of the research team or gaining financial benefit and is not acting in a professional capacity. Examples of suitable people who might act in this manner are a family member, caregiver or close friend. If a Personal Consultee is not available or is unable or unwilling to provide advice, then a **Nominated Consultee** can be approached. A Nominated Consultee is often a professional who is involved in the patient's care in a professional capacity but has no connection with the research study. These participants will not be eligible for any study procedures including DNA/RNA sample collection and relevant sections of the consent form will be marked as 'no' as directed by the instructions on the consent form. Only clinically collected data being used for participants who have not provided informed consent themselves. Participants who regain the capacity to consent for themselves will be asked to provide full informed consent. Consultee Declaration will only occur for face to face or telephone consent.

## 7.2 **Baseline Assessments**

We will collect baseline information that will include, but not be limited to:

- Patient details (e.g. name, NHS number, date of birth, biological sex, address and postcode)
- Demographic details (self-reported ethnicity, household income, gender, education level, marital status, disabilities, and exposure details). This questionnaire will be provided to participants following informed consent. This may be asked verbally face to face or over the telephone or provided as a self-completed paper questionnaire during visits or posted to participants for completion and return alongside postal consent forms. Clinician details (e.g. name)
- COVID-19 symptom onset date
- COVID-19 results of throat, nasal swab, or sputum sample, or serology from blood tests
- Pre-existing comorbidities (e.g. heart disease, diabetes, chronic lung disease, chronic kidney disease)
- Pre-existing immunosuppressants Y/N
- COVID-19 severity as assessed by need for supplemental oxygen or ventilation/extracorporeal membrane oxygenation
- Other organ support required during hospitalisation such as renal replacement therapy
- Anti-coagulant during COVID-19 hospitalisation Y/N
- Antibiotic during COVID-19 hospitalisation Y/N
- Steroid during COVID-19 hospitalisation Y/N
- Date of hospitalisation
- Date of discharge
- Name of person completing the form

**Figure 6: PHOSP and ISARIC recruitment - linked data collection and repository**

### 7.3 Subsequent Assessments

We will undertake automated repeat extraction of routine healthcare records (for example, NHS Digital) for all participants every 3 months after enrolment into the study for the first 12 months and every 6 months thereafter. Extraction time-points might vary by up to 3 months. Participants who attend additional clinic visits will have information recorded from their clinical visits as described above (section 5.2). Participants who agree to additional research procedures and sampling (Tier 2) and to additional research studies (Tier 3) will have those data recorded (as described above – sections 5.3 and 5.4). See Figure 1.

### 7.4 Recruitment and Follow-up

Recruitment will continue for one year (although current funding will be for six months). For all participants, we will continue to link to their clinic data for at least 25 years or until the patient has deceased or withdrawn consent.

Following recruitment of the first 1000 participants, we will undertake a review to determine if key populations are under-represented. Strategies needed to address under-representation will be developed and agreed by the Executive Board (Figure 7).

## **7.5 Discontinuation/Withdrawal of Participants from Study Treatment**

Each participant has the right to withdraw from the study at any time by completing a withdrawal form (this could be face to face, phone or post and online at Phosp.org). In addition, the investigator may discontinue a participant from the study at any time if the investigator considers it necessary for any reason including:

- Ineligibility (either arising during the study or retrospective having been overlooked at screening)
- Significant protocol deviation
- Consent withdrawn
- Lost to follow up (i.e. moved to a different geographical area and no longer attending the local clinics for their conditions).
- Death

The reason for withdrawal will be recorded in the CRF. The withdrawal form can be completed by someone acting on behalf of the participant.

If participants withdraw then any data and samples already collected will remain and be used in the study. Information and data will continue to be collected about participants health from central NHS records, hospital records and from participants GP unless participants state otherwise on the withdrawal form.

## **7.6 Source Data**

The source data will be hospital records (from which medical history and previous and concurrent medication information will be extracted), demographic data, health and social care records (e.g. NHS Digital, primary care health records), clinical and office charts including 'True Colours', laboratory and pharmacy records, and imaging. Source data also includes data from linked research studies.

All documents will be stored safely in secure office environments with access restricted to delegated members of the research study teams at each of the participating sites. On all study-specific documents, other than the signed consent and withdrawal forms, the participant will be referred to by the study participant number/code, not by name. For any questionnaires that are posted out, the default will be for them to be labelled by study ID only. If there are two study participants in the household the questionnaires will be named for completion but the names would be removed before filing in their research file.

## **8. SAFETY REPORTING**

As this is an observational study an adverse event in this protocol is defined as any untoward medical occurrence in a patient or clinical investigation that has occurred from research interventions only. Therefore, we will only report adverse events and serious adverse events that relate directly to participation in the study (for example, as a consequence of providing additional blood samples or physical activity monitoring). All adverse events (AEs) and serious adverse events (SAEs) will be recorded on an AE/SAE log in the ISF to capture start and end dates.

Any clinically significant results as part of the research will be shared with the participant's lead clinician or general practitioner for further action as required with the exception of results from DNA analysis (see Section 11.1 below).

## 9. STATISTICS

### 9.1 *Description of Statistical Methods*

Analyses will be performed using standard epidemiological and statistical genetics methodology. This will include cross-sectional and longitudinal studies, and analyses of disease prevalence and incidence.

Analysis design and choice of controls will be dependent upon the precise nature of the research question. Identification of risk factors for a specific COVID-19 sequela would involve controls both from within PHOSP-COVID (without the sequela) and serology-positive controls with prospective questionnaire and healthcare record linkage from Longitudinal Population Studies (for example, UK Biobank, Coronagenes, EXCEED) and pre-existing disease cohorts.

Analyses aiming to characterise and understand the clinical features, subtypes and trajectories of sequelae (for example, sarcopaenia) would evaluate the cross-sectional and longitudinal clinical data and biomarkers of PHOSP participants who are presenting with the sequelae being studied.

Analyses aiming to understand the role and function of particular biomarkers (for example, genetic markers, raised cytokine levels) would conduct 'phenome-wide' analyses of that biomarker using the full PHOSP dataset.

The PHOSP-COVID study itself is also intended as a source of cases and controls for other studies. For example, as a comparator group for studies of critical care of non-COVID-19 disease, or for studies of sequelae identified amongst non-hospitalised COVID-19 survivors. Our research Tier 3 capability enables recall of PHOSP-COVID study participants for case-control studies or nested cohort studies based on either pre-existing risk factors (for example, age, demographics, biomarkers, comorbidities) or disease status itself (for example, post-COVID-19 cardiovascular complications). PHOSP-COVID study participants are asked for consent to linkage with other research studies to which they are recruited to reduce sample overlap.

We have extensive experience of development of, and collaborative use of, disease-specific and general population cohort studies both nationally and internationally enabling access to control populations and alignment of research strategies for rapid validation and replication of findings.

### 9.2 *The Number of Participants*

We aim to recruit 10,000 individuals, who were discharged from hospital with suspected COVID-19. This will include at least 4,000 individuals that participate in Tier 2 samples and data collection.

We aim to study the impact of COVID-19 upon respiratory, cardiovascular, deconditioning and mental health. Without prior knowledge of the incidence of new chronic disease as a consequence of COVID-19 in post-hospitalised survivors it is not possible to precisely estimate whether these number of participants are sufficient to identify key associations between the development and persistence of chronic disease and demographic, clinical and molecular biomarkers of susceptibility. However, data in the small cohorts reported do provide some insights, for example, of the possible development of lung fibrosis. In SARS, abnormal diffusion capacity (a physiological measure indicating possible

underlying fibrosis) was identified in ~25% of hospitalised cases, and data from China suggests a similar decrement in diffusion capacity in COVID-19.

A sample size of 4,000 will allow an equal discovery and validation subsets in the same study to explore fibrosis risk versus non-risk using a binary regression model. This model will have 80% power to detect odds ratios >1.1 assuming the multiple correlation coefficient  $\rho$  to be approximately 0.4, the event rate to be 0.25. A sample size of 500 will have 80% power to detect an odds ratio >1.5. Thus, we are confident that we will have sufficient power to identify important associations between risk biomarkers and development of different chronic diseases in important subgroups e.g. ethnicity or those receiving specific interventions during the acute infection.

Where recall studies are proposed (Research Tier 3), the Executive Board will review experimental design and power calculations to ensure adequate sample sizes are included and proposals will be approved by the External Scientific Advisory Board (Figure 7) and will undergo ethical review as appropriate.

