### **9.3 The Level of Statistical Significance**

Statistical significance thresholds will be defined in advance of each analysis and will take into account issues of multiple testing and *a priori* evidence.

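### Section 9.2 quotes 80% power at an odds ratio of 1.1 without allowing for the discovery/validation split; under standard assumptions each half of 2,000 has about 39% power there and supports about 1.17

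*Protocol*

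**What the plan says.** Section 9.2 of the protocol sets out the design in one sentence: "A sample size of 4,000 will allow an equal discovery and validation subsets in the same study", with the purpose "to explore fibrosis risk versus non-risk using a binary regression model". The next sentence gives the result: "This model will have 80% power to detect odds ratios >1.1". Its inputs are a multiple correlation coefficient taken "to be approximately 0.4, the event rate to be 0.25". A companion figure follows: "A sample size of 500 will have 80% power to detect an odds ratio >1.5". From these the section concludes that power will be sufficient to find "important associations between risk biomarkers and development of different chronic diseases", including in subgroups.

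No alpha, sidedness or predictor scale is given. Section 9.3 says only: "Statistical significance thresholds will be defined in advance of each analysis and will take into account issues of multiple testing".

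**The concern.** If the 4,000 are split equally, each model is fitted to 2,000 people. The power sentence follows directly on the split, yet it names no sample size of its own and makes no allowance for halving. A reader can take 1.1 as the effect that the discovery analysis, and then the validation analysis, can each find with 80% power.

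This is the only power calculation in the protocol, and the section's statement of confidence rests on it. If the halves do not have the stated power, a null result for a modest association in either half carries less information than section 9.2 suggests.

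**Working it through.** **Inputs from section 9.2:** event rate p = 0.25; multiple correlation 0.4, so R² = 0.16; power 80%; odds ratio (OR) 1.1; n = 4,000, or 2,000 per half; companion figure OR 1.5 at n = 500.

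**Assumptions, because the protocol is silent:** two-sided 5%; a continuous predictor with the OR expressed per standard deviation (SD). Alternatives are shown below.

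**Formula** (logistic regression, variance inflated for correlation with other covariates):

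n = (z_α + z_power)² / [p(1−p) × (ln OR)² × (1−R²)]

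**1. Attempt to reproduce the stated figure.** p(1−p)(1−R²) = 0.1875 × 0.84 = 0.1575. ln 1.1 = 0.0953. Then n = (1.960 + 0.8416)² / (0.1575 × 0.0953²) ≈ 5,486. The stated 80% at exactly 1.1 is not reproduced with 4,000.

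**2. Power at OR 1.1**, as Φ(√(n × 0.1575) × ln 1.1 − 1.96):
- n = 4,000: Φ(25.10 × 0.0953 − 1.96) = Φ(0.43) = 66.7%
- n = 2,000: Φ(17.75 × 0.0953 − 1.96) = Φ(−0.27) = 39.4%

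Simulated logistic fits (1,500 runs each) gave 66.7% and 38.7%.

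**3. OR detectable with 80% power**, as exp[2.8016 / √(n × 0.1575)]: 1.118 on 4,000, 1.171 on 2,000, 1.371 on 500.

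**4. Other readings of the unstated inputs**

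| Reading | Power at 1.1: 4,000 / 2,000 | Detectable OR: 4,000 / 2,000 / 500 |
|---|---|---|
| Two-sided, R² = 0.16 | 66.7% / 39.4% | 1.118 / 1.171 / 1.371 |
| One-sided, R² = 0.16 | 77.3% / 51.9% | 1.104 / 1.150 / 1.323 |
| Two-sided, 0.4 read as R² | 52.5% / 29.8% | 1.141 / 1.205 / 1.453 |
| Two-sided, correlation ignored | 74.2% / 45.5% | 1.108 / 1.156 / 1.336 |
| One-sided, correlation ignored | 83.3% / 58.0% | 1.095 / 1.137 / 1.293 |
| Two-sided, R² = 0.16, 50:50 binary predictor | 22.2% / 13.3% | 1.250 / 1.371 / 1.880 |

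None of these readings reaches 80% at 1.1 on 2,000. One reaches it on 4,000, and it discards the stated correlation.

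**5. Consistency with the figure for 500.** With the other inputs fixed, the detectable ln OR is proportional to 1/√n, whatever the alpha, correlation or predictor scale. Taken as exact, 1.1 and 1.5 imply a sample-size ratio of (ln 1.5 / ln 1.1)² = 18.1. The protocol's ratio is 4,000/500 = 8, or 2,000/500 = 4 if 1.1 refers to a half.

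Now allow one-decimal rounding. The smallest ratio that still prints as 1.1 and 1.5 is about (ln 1.45 / ln 1.149)² = 7.2. A ratio of 8 is therefore possible and a ratio of 4 is not. Reading 0.4 as R² gives 1.141 on 4,000 and 1.453 on 500, which round to both printed values.

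**6. The figure for 500.** Power at OR 1.5 is Φ(√(500 × 0.1575) × ln 1.5 − 1.96) = Φ(1.64) = 94.9%, or 86.0% if 0.4 is R². The claim made there is met with room to spare.

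**The case against.** The strongest defence is rounding. The section prints odds ratios to one decimal, and on all 4,000 the detectable value of 1.118 (1.104 one-sided) rounds to 1.1. That stands: a reader might infer that the full 4,000 is materially underpowered, and the documents do not support this. Nor do they support calling 1.1 and 1.5 irreconcilable, since reading 0.4 as R² gives both after rounding. That reading, however, uses all 4,000 and sits badly with the protocol's term for the coefficient. Rounding does not rescue the halves: 1.171 prints as 1.2. In the table, only one-sided testing with the correlation dropped (1.137) would print as 1.1 on 2,000.

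Second, alpha and predictor scale are assumptions of this check. An OR per SD is a convention, not the most favourable case. If the OR is per measured unit and the predictor's SD is about 1.17 units, 4,000 gives 80% power at 1.1; at about 1.66 units, 2,000 does. This stands as a limit on the conclusion, but the protocol names no unit, and the multiplicity adjustment promised in section 9.3 works the other way.

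Third, the section admits that sufficiency cannot be estimated precisely, and offers fibrosis as an example in an observational platform. That is fair, but a conditional calculation should still follow from its own stated conditions.

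Two further inferences go too far. A true OR of 1.1 would not almost never be confirmed: power in the validation half is about 39%, and the lower figure of about 16% (0.394²) is the chance of significance in both halves. Nor does the shortfall show that the split is wrong. Independent replication of a biomarker association is a legitimate aim, which resampling on the full set does not replace.

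**Conclusion.** The point holds for the halves. Under two-sided 5% and an OR per SD, a subset of 2,000 has about 39% power at 1.1 and detects about 1.17 with 80% power. If 0.4 is R², these become 30% and 1.21; one-sided, 52% and 1.15. On all 4,000 the power at exactly 1.1 is about 67%, but the detectable OR of about 1.12 agrees with the printed figure after rounding. The 1.1 and 1.5 figures conflict as exact values and can be reconciled by rounding only if 1.1 refers to the undivided 4,000, in which case the section gives no power for the split analysis it plans. The figure for 500 understates the power available and is not itself a shortfall. All power values rest on the assumed alpha and predictor scale; the scaling argument between the two figures does not.

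**What to change.** Restate the power paragraph in section 9.2 with alpha, sidedness, predictor scale, whether 0.4 is a correlation or an R², and the sample size each figure refers to. For example:

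*With two-sided alpha 0.05, event rate 0.25, rho 0.4 (R² = 0.16) and odds ratios per SD, each subset of 2,000 has 80% power for an odds ratio of about 1.17, the full 4,000 for about 1.12, and 500 for about 1.37. Multiplicity-adjusted thresholds (section 9.3) will raise these values.*

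If the authors meant R² = 0.4, the corresponding values are about 1.21, 1.14 and 1.45. Keep the discovery/validation split. The cost is one reworded paragraph and a slightly less favourable stated figure; no extra participants are needed.
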